7.4 AE classification according to frequency

- Once: the AE occurred only once;
- Continuous: AE persists or worsens, without resolution between treatment courses or cycles;
- Intermittent: AE occurs and resolves during one treatment cycle/course, and then occurs again in another treatment cycle/course.

7.5 AE classification according to intensity

The AEs will be considered as serious (SAEs), regardless of the administered medication dose, in situations that result in any of the following clinical outcomes:

- Deaths;
- Life-threatening; there is a risk of death at the time of the event;
- Hospitalization or prolongation of existing hospitalization: hospitalization will be considered as hospital care requiring participant admission, as well as their stay for a period less than 24 hours in a hospital unit;
- Significant or persistent disability: substantial interruption of a person's ability to perform normal life functions;
- Congenital anomaly and birth defect;
- Any suspicion of transmission of an infectious agent through a drug;
- Clinically significant event: any event resulting from drug use that requires medical intervention to avoid death, life-threatening situations, significant disability, or hospitalization.

All situations that do not result in the clinical outcomes mentioned above will be considered as non-serious AEs.

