7.10 Ethics Committee notification

The research Ethics Committee (EC) must be notified of all Serious Adverse Events (SAEs) occurring with the research participant from the center under its responsibility within a maximum period of 24 hours, after the center becomes aware of the event through its responsible investigators.

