7.12 Clinical Research Center notification to Sponsor

Non-serious AE reports should be forwarded to the Sponsor's Clinical Research Department through the AE pages in the CRF by the clinical research monitor after monitoring has been conducted.

Serious AE reports should be sent to the Sponsor within 24 hours of the Research Center's knowledge via the specific AE reporting form provided by the Study Sponsor. This form should be sent to the Clinical Study Monitor and to the Sponsor.

This submission to the Sponsor's Clinical Research Department is independent of the relationship between the AE and the investigational product.

7.13 Consistency of the data shared from the Clinical Research Center to the Sponsor

If there are any inconsistencies in the information about the AE in the CRFs or forms, a clarification note will be sent by email directly to the Investigator responsible for recording the AE for updates. A follow-up will be scheduled with the Investigator to monitor the progress of the condition.

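### One of the seven seriousness criteria in section 7.5 applies only to drug-caused events, so some events judged unrelated lose 24-hour reporting

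*Combined protocol and SAP*

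**What the plan says.** Section 7.5 is headed as a classification of intensity but defines seriousness. It lists seven criteria. Death, life-threatening event, hospitalization, disability and congenital anomaly are defined by outcome alone. A sixth, suspected transmission of an infectious agent, names a drug as the route because that is its subject. The seventh is worded "Clinically significant event: any event resulting from drug use that requires medical intervention to avoid death, life-threatening situations, significant disability, or hospitalization". The section closes with a default: "All situations that do not result in the clinical outcomes mentioned above will be considered as non-serious AEs".

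Two reporting rules depend on that classification:

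- Section 7.12: "Serious AE reports should be sent to the Sponsor within 24 hours". Non-serious AEs go on CRF pages, forwarded "by the clinical research monitor after monitoring has been conducted". The section adds that submission to the sponsor "is independent of the relationship between the AE and the investigational product".
- Section 7.10: the Ethics Committee "must be notified of all Serious Adverse Events (SAEs) occurring with the research participant", also within 24 hours. No comparable route is given for non-serious AEs.

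Section 7.1 has every AE after consent entered in the CRF whatever its cause. Section 9 says each AE will be described, including whether it was serious, and gives its own list in brackets: death, abortion, immediate risk of death, hospitalization or its prolongation, and disability.

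**The concern.** Seriousness and causality answer different questions. Seriousness decides how fast someone outside the site looks at an event. Causality is one of the things that person then checks. If a seriousness criterion already contains a causal condition, the site's first opinion on cause can settle whether the early outside look takes place.

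This matters more than usual here. The study is described in section 3.1 as the first human trial of the formulation, safety and tolerability are a primary goal (2.1), and only 12 people will be treated. An effect of the product that nobody has yet recognised is the kind of event a site may attribute to something else, such as the catheter, the blood draws or an intercurrent illness. The error also has a fixed direction: the condition can take events out of the serious category but cannot add any.

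**Working it through.** No arithmetic applies, and the plan states no figure on this point. The check is to run different events through section 7.5 as written and see where each one lands. Every event below needs medical intervention.

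1. **Risk of death when it occurred, judged unrelated.** Serious, because the criterion "Life-threatening; there is a risk of death at the time of the event" carries no causal condition. The 24-hour reports apply.
2. **Admitted, or a short hospital stay, judged unrelated.** Serious. Hospitalization has no causal condition and covers admission "as well as their stay for a period less than 24 hours in a hospital unit". The 24-hour reports apply.
3. **Treated without any hospital stay, so as to avert hospitalization or disability, judged to come from drug use.** Serious under the seventh criterion. The 24-hour reports apply.
4. **The same clinical course as case 3, judged not to come from drug use.** The seventh criterion fails on its causal condition. There was no death, no risk of death at the time, no hospital stay, no significant disability, no congenital anomaly and no suspected transmission of an infectious agent, so no other criterion is met. The closing sentence of 7.5 makes it non-serious.
5. **Treated to avert a death that was not yet a risk at the time, no hospital stay, judged unrelated.** Non-serious by the same route as case 4, though this combination should be uncommon.

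Cases 3 and 4 differ only in the opinion on cause, so the gap is real.

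Next, does any other section close it?

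- **7.12.** Its statement on independence governs the sending of reports. The 24-hour limit applies to reports already classed as serious, and case 4 never gets that far.
- **7.10.** It covers SAEs only, so case 4 does not go to the Ethics Committee.
- **7.1 and 7.7.** The event and any treatment given are recorded, so the information exists at the site. Neither section sets a deadline for it to reach the sponsor.
- **7.6.** Section 7.5 does not say how drug causation is to be decided and does not cite 7.6. If 7.6 is used, Chart 5 places an event with fitting timing, another cause and no known effect in the lowest category, which counts as not related. Events that are non-evaluable are assigned to neither related nor not related, so their position under the seventh criterion is undefined.
- **Section 9.** Its bracketed list contains no medically significant criterion at all, and also omits congenital anomaly and infectious transmission. Applied literally, it would describe case 3 as well as case 4 as non-serious in the results. Correcting 7.5 alone would therefore leave the reported classification unresolved.

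**The case against.** The strongest case on the other side is that the affected set of events is small and its consequences are limited. Most of that stands.

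- **A reader might infer that causality decides seriousness throughout 7.5.** It does not. The causal condition limits one criterion of seven.
- **A reader might infer that an event needing treatment to prevent death is easily filed as non-serious.** Mostly it is not. Cases 1 and 2 show that a risk of death at the time, or any hospital stay, makes the event serious whatever its cause. Only case 5 remains.
- **A reader might infer that 7.5 contradicts 7.10 and 7.12.** It does not do so literally. Those sections say what happens to SAEs and do not define them, so a site can follow all three. What can fairly be said is that 7.5 works against the purpose of 7.12.
- **A reader might infer a distorted SAE rate.** Section 9 plans no rate. It plans a qualitative description of every AE, with its mode of resolution and causality, so the event stays visible in the results.
- **Regulator reporting would change little.** Apart from fatal or life-threatening events, 7.11 covers unexpected serious events only when causality is at least possible. An event rated not related would fall outside it in any case.
- **The words refer to drug use, not to the investigational product.** Some procedure-related events might qualify: the PK catheter is flushed with sodium heparin (5.3.1), so bleeding at the site could be read as drug-caused. This narrows the gap under one reading. It also shows that the criterion can be read in more than one way, which is a further reason to reword it.

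None of these points brings case 4 back into 24-hour reporting.

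**Conclusion.** The point holds in a limited form. An event falls through section 7.5 when all of the following are true: it needed intervention to avert one of the listed outcomes; there was no risk of death at the time; there was no admission or hospital stay; no significant disability resulted; and it was judged not to come from drug use. It stays in the CRF and in the descriptive results. It loses the 24-hour report to the sponsor and to the Ethics Committee, and moves to a route with no stated deadline.

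The documents give no basis for estimating how often this would happen among 12 healthy participants, so no frequency is claimed.

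The conclusion rests on two assumptions: that the criterion is applied as written, and that treatment at the research centre does not itself count as a stay in a hospital unit, which the protocol does not say. If such treatment did count, the gap would shrink further. It remains worth correcting, because the error runs only towards fewer SAEs and the remedy is a small wording change.

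**What to change.** Make three wording changes, to be carried through to the SAE form:

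1. In 7.5, replace the opening of the seventh criterion, which limits it to drug-caused events, with *any AE, regardless of causal relationship, that requires medical intervention*. Leave the rest of the criterion as it is.
2. State in 7.5 that causality is assessed separately under 7.6 and does not decide seriousness.
3. Align the seriousness list in section 9 with 7.5, preferably by citing 7.5 instead of keeping a second list, and reconcile the item that appears only in section 9 (abortion).

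The cost is the text edits and at most a few more SAE forms. No visits, tests or participants are added, and clinical management is unchanged; only classification and reporting are affected.

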7.6 AE classification according to causality

To determine causality, the Investigator should use the World Health Organization's (modified) system. In this way, three criteria will be evaluated to define the causal relationship:

- Temporal relationship - The AE occurred after the use of the investigational product (IP), within at least 10 times its half-life;
- Other causes - Strong presence of other causes that may be related to the AE;
- Known effect - The effect is known or physiologically related to any of the components of the IP.

CHART 5. MONITORING OF THE IP THROUGHOUT THE STUDY

| Classification | Time related | Other causes | Known effect |
|----------------|--------------|--------------|--------------|
| Improbable | No | NA | NA |
| | Yes | Yes | No |
| Possible | Yes | No | No |
| | Yes | Yes | Yes |
| Probable | Yes | No | Yes |

- Probable: a reaction that follows a reasonable temporal sequence between medication administration and the appearance of the AE. It follows a known pattern of response to the suspected medication. It cannot be reasonably explained by the participant's known clinical state characteristics.

- Possible: a reaction that follows a reasonable temporal sequence between medication administration and the appearance of the AE. It follows a known pattern of response to the suspected medication, but it could have been produced by the participant's clinical state or other therapies administered concomitantly.
- Unlikely: a reaction that does not follow a reasonable temporal sequence between medication administration and the appearance of the AE; or that does not follow a known pattern of response to the IP, and can be explained by the participant's known clinical state characteristics.

If there is not enough data available to correctly establish the causality of the AE (due to insufficient evidence, conflicting data, or poor documentation), the Investigator should classify it as **non-evaluable**.

AEs classified as "Probable" and "Possible" will be considered "related" to the PSI, and those classified as "Unlikely" will be considered "not related".

7.7 Information regarding the action taken regarding the IP

The investigator must report in both source documents and the participant's CRF what action was taken regarding the use of the IP at the time they became aware of the AE. The investigator must report if there was a need for clinical, pharmacological, or surgical treatment, as well as any other medical management required to resolve the presented AEs.

7.8 Information regarding participants development

The investigator must report the evolution of the condition (clinical outcome), considering the following progression:

- Recovered: when the AE is no longer present;
- Recovering: when the AE is present but improving compared to its initial state;
- Not recovered: when the AE is present and/or getting worse;
- Recovered with sequelae: when the AE is no longer present, but the patient presents associated sequelae;
- Ignored: when the condition of the AE is unknown;
- Death: when the AE in question has led the patient to death.

In cases of death, it is essential to record the date related to cause of death, to provide a death certificate, or medical autopsy report, when possible.

7.9 AE reports follow-up

The Investigator shall monitor the symptoms presented, whether or not they are related to the IP. This monitoring should be continued until the symptoms disappear or if they persist, the Investigator should initiate classical medical procedures to treat the symptom and evaluate the participant's continued participation in the study. A follow-up report shall be submitted to the Sponsor, with data regarding the monitoring of these reports, in accordance with current regulations.

7.10 Ethics Committee notification

The research Ethics Committee (EC) must be notified of all Serious Adverse Events (SAEs) occurring with the research participant from the center under its responsibility within a maximum period of 24 hours, after the center becomes aware of the event through its responsible investigators.

7.11 ANVISA notification

The sponsor must ensure that all relevant information about unexpected serious adverse events that are fatal or life-threatening occurring in the national territory are documented and notified to ANVISA, through an electronic form within a maximum of 7 (seven) consecutive days from the date of knowledge of the case by the sponsor. In addition, additional information about the follow-up of these adverse events must be included in the form within 8 (eight) consecutive days from the date of notification. All other serious unexpected adverse events, whose causality is possible, probable, or definite in relation to the investigational products, must be reported to ANVISA within 15 (fifteen) consecutive days from the date of knowledge of the case by the sponsor.

7.12 Clinical Research Center notification to Sponsor

Non-serious AE reports should be forwarded to the Sponsor's Clinical Research Department through the AE pages in the CRF by the clinical research monitor after monitoring has been conducted.

Serious AE reports should be sent to the Sponsor within 24 hours of the Research Center's knowledge via the specific AE reporting form provided by the Study Sponsor. This form should be sent to the Clinical Study Monitor and to the Sponsor.

This submission to the Sponsor's Clinical Research Department is independent of the relationship between the AE and the investigational product.

7.13 Consistency of the data shared from the Clinical Research Center to the Sponsor

If there are any inconsistencies in the information about the AE in the CRFs or forms, a clarification note will be sent by email directly to the Investigator responsible for recording the AE for updates. A follow-up will be scheduled with the Investigator to monitor the progress of the condition.

7.14 Financing and Insurance

The Investigator, the Sponsor, and the institutions and/or organizations involved in the different phases of the research must provide immediate assistance, as well as take responsibility for the comprehensive care of the research participants regarding the complications and damages arising from the research.

8. ETHICAL ASPECTS / HUMAN PROTECTION

This research protocol was designed according to resolution 466/12 and subsequent regulations. Researchers must ensure that this study is conducted in full compliance with the principles of the "Helsinki Declaration", the principles described in the "Guidelines for Good Clinical Practice" of the International Conference on Harmonization (ICH), and the regulations of resolution 466/12.

8.1 Ethical Committee

The clinical study must be previously approved in writing, according to applicable legislation, by an Ethics Committee (EC) indicated by the National Commission for Ethics in Research (CONEP) through the issuance of a Substantiated Opinion. The submission of the clinical study protocol to the EC is the responsibility of the Principal Investigator, as well as the monitoring of the status of this evaluation. No activity involving research participants may be initiated before the approval of this clinical protocol by the EC.

Any changes to the clinical protocol as well as to the informed consent form (ICF), or any other written information provided to research participants, must be previously approved by the CEP, with the new approval of this documentation being forwarded to the Sponsor. Records of review and approval of all documents related to the study must be filed by the Investigator, since they may be requested in inspections carried out during and after the study.

8.2 ICF

The Investigator will protect the integrity of the participants, following all applicable regulations.

It is the responsibility of the researcher, or a person designated by the researcher, to obtain the signed informed consent form (ICF) from each patient, before any study-related procedures are performed. The participant must be informed of all pertinent aspects of the study and the elements of the ICF, including the objectives, methods, anticipated benefits, and potential risks of the study. The participant should have sufficient time to ask questions and think about the decision to participate or not. If the participant agrees to voluntarily participate in the study, they must sign and date two copies of the same approved version of the ICF provided by the EC.

The researcher or designated person must also explain that patients are entirely free to refuse to be included in the study or to withdraw from it at any time, for any reason.

The ICF used during the study must be reviewed by the Sponsor, approved by the EC, and made available for inspection. If new safety information results in significant changes in the risk/benefit assessment, the ICF must be reviewed and updated, if necessary. All patients (including those already being treated) must be informed of the new information, provided with a copy of the revised form, and give their consent to continue in the study.

8.3 Participant confidentiality

Considering the privacy of the research participant, all data related to the participant will be identified only by the initials of their name and the corresponding code for the clinical study phase. All personal data will be omitted in any analysis of results.

However, it is necessary for the Investigator to allow the study monitor (in the presence or absence of the Investigator) to review the part of the research participant's records related to the clinical study. This should include all documentation containing the research participant's medical history to verify eligibility, laboratory test results, diagnoses, summaries of the research participant's admission or non-admission to the hospital during the period of the clinical study, as well as death certificates and/or autopsy reports.

8.4 Confidential Information and Publications

Confidential Information is considered for any and all information that has not been previously published and provided to the Investigator and members of their team by the Sponsor. This includes, but is not limited to, the investigator's brochure, basic scientific data, clinical research protocol, amended protocols/amendments (when applicable), case report forms, and experimental methods. Any data obtained during the course of the clinical study is also considered confidential. All confidential information is the property of the Sponsor, however, it will be available to government health authorities.

At the end of the clinical study, after data analysis and submission to regulatory authorities, the results will be published by the Sponsor following the current regulations in the country.

8.5 Risk/benefit analysis

8.5.1 Expected benefits

This is a phase 1 study in healthy individuals, so individual benefits are not expected. This study may benefit many patients in the future if the proposed intervention proves to be safe and effective.

8.5.2 Risks related to the intervention

Pre-clinical studies did not demonstrate any occurrence of local or systemic side effects related to the IP. Therefore, possible adverse effects for IP are limited to the possibility of local reactions such as allergy, irritation or sensitivity, which may manifest as skin rash, urticaria and edema; and effects based on vasodilation resulting from products that act on the NO pathway, such as hypotension, headache and priapism.

Regarding procedures, blood collection may cause bruising. The participant will fast for blood collection at V-1.

8.5.3 Contraceptives methods

To avoid any safety issues for research participants, the following contraceptive methods will be considered acceptable when used correctly: oral contraceptives, contraceptive patches and/or injections, male condoms, diaphragms or cervical caps with spermicide, contraceptive vaginal ring, intrauterine device, surgical sterilization (bilateral tubal ligation, vasectomy), or sexual abstinence.

The Investigator and the participant will decide on the appropriate contraceptive method to be used.

8.6 Safety monitoring

8.6.1 Study Suspension

The Sponsor may suspend or terminate a study, or part thereof, at any time, for any reason. After the decision to suspend or cancel, the Sponsor must notify the Ethics Committee within a maximum of 15 calendar days, except in cases of temporary suspension as a safety measure, when the deadline is 7 calendar days from the date of suspension. It should be noted that cancellations under RDC 09/2015 are final and apply only to ongoing clinical trial protocols, with no possibility of reactivation later.

If the Investigator suspends or terminates the study, he/she must immediately inform the Sponsor and the Ethics Committee and provide them with detailed written information. The Investigator shall also return to the Sponsor all investigational products, their containers, and other study materials.

Upon completion of the study, the Investigator shall provide the Sponsor and the Ethics Committee with final reports and summaries, as required by applicable regulations.

